## **2.8. Statistical Considerations**

This section summarizes the planned statistical analysis strategy and procedures for the study. The details of statistical analysis will be provided in a statistical analysis plan (SAP), which will be finalized before the database lock for the study. If changes are made to primary and/or secondary objectives or related statistical methods after the study has begun, then the protocol will be amended (consistent with ICH Guideline E9). Changes to other secondary or exploratory analyses made after the protocol has been finalized, along with an explanation as to when and why they occurred, will be listed in the SAP or CSR for the study. Ad hoc exploratory analyses, if any, will be clearly identified in the CSR.

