The number and percentage of participants with seroresponse or seroconversion at each postbaseline timepoint will be provided with 2-sided 95% CIs using the Clopper-Pearson method. For the co-primary endpoint and key secondary endpoints regarding SRR and SCR, the Miettinen-Nurminen's method will be used to calculate the 95% CI for the difference in the SRR or SCR at Day 29 between the vaccination groups. The noninferiority of the SRR at Day 29 for RSV-A/RSV-B nAbs will be demonstrated if the LB of the 95% CI of the SRR difference between mRNA-1345 + Afluria Quadrivalent coadministered and mRNA-1345 plus placebo groups is  $> -10\%$ . The noninferiority of the SCR at Day 29 will be demonstrated if the LB of the 95% CI of the SCR difference between mRNA-1345 + Afluria Quadrivalent coadministered and Afluria Quadrivalent plus placebo groups is  $> -10\%$ .

Data from quantitative immunogenicity assays will be summarized for each vaccination group using positive response rates and geometric means with 95% CIs for each timepoint an assessment is performed.

For the immunogenicity endpoints, the GMT/GMC ratio of specific Abs, with the corresponding 95% CI at each timepoint, and geometric mean fold rise of specific Ab titers, with the corresponding 95% CI at each postbaseline timepoint over preinjection baseline on Day 1, will be provided by vaccination group. The 95% CIs will be calculated based on the t-distribution of the log-transformed values then back-transformed to the original scale descriptive summary statistics, including the median, minimum, and maximum values, will also be provided.

For summarizations of the GMT/GMC ratios, Ab titers reported as below the LLOQ will be replaced by  $0.5 \times$  LLOQ. Values that are greater than the upper limit of quantification (ULOQ) will be converted to the ULOQ if actual values are not available.

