SRR of RSV-A nAbs, RSV-B nAbs, or a SARS-CoV-2 strain nAbs is defined as proportion of participants with post-vaccination titers  $\geq 4 \times$  LLOQ if baseline is  $<$  LLOQ or a  $\geq 4$ -fold increase from baseline if baseline is  $\geq$  LLOQ. The number and percentage of participants with seroresponse at each postbaseline timepoint will be provided with 2-sided 95% CIs using the Clopper-Pearson method. For the co-primary endpoint and key secondary endpoints regarding SRR, the Miettinen-Nurminen's method will be used to calculate the 95% CI for the difference in the SRR at Day 29 between the vaccination groups. The noninferiority of the SRR at Day 29 for RSV-A nAbs or RSV-B nAbs, will be demonstrated if the LB of the 95% CI of the SRR difference between mRNA-1345 plus mRNA-1273.214 followed with a subsequent injection of placebo and mRNA-1345 plus placebo followed with a subsequent injection of mRNA-1273.214 groups is  $> -10\%$ . The noninferiority of the SRR at Day 29 for nAbs of SARS-CoV-2 Wuhan-Hu-1 or B1.1.529 strain will be demonstrated if the LB of the 95% CI of the SRR difference between mRNA-1345 plus mRNA-1273.214 followed with a subsequent injection of placebo and mRNA-1273.214 plus placebo followed with a subsequent injection of placebo groups is  $> -10\%$ .

Data from quantitative immunogenicity assays will be summarized for each vaccination group using positive response rates and geometric means with 95% CIs for each timepoint an assessment is performed.

For the immunogenicity endpoints, the GMT ratio or GMC ratio of specific Abs, with the corresponding 95% CI at each timepoint, and GMFR of specific Ab titers, with the corresponding 95% CI at each postbaseline timepoint over preinjection baseline, will be provided by vaccination group. The 95% CIs will be calculated based on the t-distribution of the log-transformed values then back-transformed to the original scale descriptive summary statistics, including the median, minimum, and maximum values, will also be provided.

For summarizations of the GMT ratios or GMC ratios, Ab titers reported as below the LLOQ will be replaced by  $0.5 \times$  LLOQ. Values greater than the ULOQ will be converted to the ULOQ if actual values are not available.

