## DOCUMENT HISTORY

Version	Date	Description of major modifications
CCI		

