## **1. Introduction**

This SAP is based on CSP (Amendment 5, dated on 16-June-2023) and approved eCRF (version 16.038, dated on 01-August-2023).

In addition to the information presented in the statistical consideration sections of the protocol (Sections 2.8, 3.8, and 4.8) which provides the principal features of analyses for this study, this SAP provides statistical analysis details/data derivations. It also documents modifications or additions to the analysis plan which are not “principal” in nature and result from information that was not available at the time of protocol finalization. If the methods in this SAP differ from the methods described in the protocol, the SAP will prevail.

Study mRNA-1345-P302 is a Phase 3, randomized, observer-blind, study to evaluate safety, tolerability, and immunogenicity of mRNA-1345, an mRNA vaccine targeting RSV, when given alone or coadministered with a seasonal influenza vaccine or SARS-CoV-2 vaccine and when given as an open-label boost at 1 Year following a primary dose in adults  $\geq$  50 years of age.

PPD Biostatistics and programming team, designee of Moderna Biostatistics and Programming department, will perform the statistical analysis. SAS Version 9.4 or higher will be used.

In this document, injection and dose are used interchangeably.

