## **2.5. Statistical Analysis**

### **2.5.1. General Considerations**

The Schedule of Assessments is provided in [Appendix F](#).

**Continuous variables** will be summarized using the following descriptive summary statistics: the number of participants (n), mean, standard deviation (SD), median, minimum (min), and maximum (max). For the summary statistics of all numerical variables, unless otherwise specified, the display precision will follow programming standards. Please see [Appendix A](#) for variable display standards.

**Categorical variables** will be summarized using counts and percentages. When count data are presented, the percentage will be suppressed when the count is zero to draw attention to the non-zero counts. A row denoted “Missing” will be included in count tabulations where specified on the shells to account for dropouts and missing values. The denominator for all percentages will be the number of participants in that vaccination group within the analysis set of interest, unless otherwise specified.

**Baseline value** is defined as the most recent non-missing measurement (scheduled or unscheduled) collected before the first injection, unless otherwise specified. For immunogenicity tests, the baseline is defined as the most recent non-missing result/measurement (scheduled or unscheduled) collected before or on the date of the first injection (Day 1). If there are multiple valid results on the same date, the largest value will be considered in the immunogenicity baseline derivation.

**Study day relative to the Day 1 injection** will be calculated as below:

- a) Study day prior to the Day 1 injection will be calculated as: date of assessment/event – date of the Day 1 injection (resulting in negative study day).
- b) Study day on or after the date of the Day 1 injection will be calculated as: date of assessment/event – date of the Day 1 injection + 1.

For GMT and GMC calculation, antibody values reported as below the LLOQ will be replaced by  $0.5 \times \text{LLOQ}$  and antibody values greater than the ULOQ will be converted to the ULOQ.

**Unscheduled visits:** Unscheduled visit measurements will be included in analysis as follows:

- In the derivation of baseline measurements.
- In scheduled visit windows per specified visit windowing rules.
- In individual participant data listings as appropriate.

**Visit windowing rules:** The analysis visit windows for protocol-defined visits are provided in [Appendix B](#), Table 5.

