### 3.5. Statistical Analysis

#### 3.5.1. General Considerations

Please see [Section 2.5.1](#) for details. Differences for Part B are listed as the following:

The Schedule of Assessments is provided in [Appendix G](#).

**Study day relative to the Day 1 injection** will be calculated as below:

- a) Study day prior to the Day 1 injection will be calculated as: date of assessment/event – date of the Day 1 injection (resulting in negative study day);
- b) Study day on or after the date of the Day 1 injection will be calculated as: date of assessment/event – date of the Day 1 injection + 1.

**Study day relative to the most recent injection** will be calculated as below:

- a) study day prior to the Day 1 injection will be calculated as: date of assessment/event – date of the Day 1 injection;

Confidential

- b) study day on or after the date of the Day 1 injection but before the Day 29 injection (if applicable) will be calculated as: date of assessment/event – date of the Day 1 injection + 1;
- c) study day on or after the date of the Day 29 injection will be calculated as: date of assessment/event – date of the Day 29 injection + 1; if study day is on the same day as the Day 29 injection, date and time will be compared with the Day 29 injection date and time. If it is prior to the Day 29 injection, then study day is calculated as bullet point b); if it is after the Day 29 injection or the time is missing or not available then study day is calculated as: date of assessment/event – date of the Day 29 injection + 1.

**Visit windowing rules:** The analysis visit windows for protocol-defined visits are provided in [Appendix B Table 6](#).

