## 5. Changes from Planned Analyses in Protocol

The following changes from planned analyses in the study protocol are included in this document:

- Appendix 6.8 Estimands and Estimand Specification: Estimands language has been added for primary immune endpoint and primary safety endpoint.
- Supportive analyses of primary and key secondary immunogenicity endpoints on Supportive PP Set are added in Part A.
- [Section 4.4.1](#) Part C Enrolled Set: Exclude screen failure from Part C Enrolled Set.
- [Section 4.5.4.3](#) Analysis of the Secondary Immunogenicity Endpoints: Methods of calculating 95% CI of paired SRR difference in Part C is updated as linear probability model.

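### For Parts A and B the SAP sets every titer above the ULOQ to the ULOQ, where the protocol does so only if no actual value exists, and SAP Section 5 does not list the change

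*SAP*

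**What the plan says.** **Protocol.** Section 2.8.5.1 (Part A): "Values that are greater than the upper limit of quantification (ULOQ) will be converted to the ULOQ if actual values are not available". Section 3.8.1.1 (Part B): "Values greater than the ULOQ will be converted to the ULOQ if actual values are not available". Section 4.8.5.1 (Part C) replaces titers above the ULOQ without any condition. Section 2.8 adds: "If changes are made to primary and/or secondary objectives or related statistical methods after the study has begun, then the protocol will be amended".

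**SAP.** Section 2.5.1, on GMT and GMC calculation: "antibody values greater than the ULOQ will be converted to the ULOQ". No condition is attached. Section 3.5.1 refers Part B to Section 2.5.1 with the words "Differences for Part B are listed as the following", and no ULOQ difference follows. Section 4.5.1 does the same for Part C.

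**Precedence and disclosure.** SAP Section 1: "If the methods in this SAP differ from the methods described in the protocol, the SAP will prevail". SAP Section 5 opens "The following changes from planned analyses in the study protocol are included in this document" and names four items: the estimands, the Supportive PP Set analyses, the Part C Enrolled Set, and the method for the Part C paired SRR difference. The ULOQ rule is not among them. The SAP's document history has a column headed "Description of major modifications", but its entries are redacted.

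**The concern.** The rule feeds the GMT and GMC comparisons. These are five of the six co-primaries in Part A (RSV-A and four influenza strains) and three of the six in Part B (RSV-A and two SARS-CoV-2 strains). Each is a non-inferiority test of the GMR against 0.667.

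That the rule reaches the ANCOVA is an inference. It is a natural one, because SAP Section 2.5.4.2.1 presents the model's back-transformed mean as the estimate of the GMT.

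If coadministration lowers titers, fewer coadministration values than reference values lie above a common cap. Capping then removes more from the reference mean, and the GMR moves toward 1. In a non-inferiority test, that bias makes it easier to pass when the true ratio is too low. A change with that direction, in a plan that overrides the protocol, belongs in the list of changes.

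**Working it through.** **1. Text comparison.** Parts A and B: protocol conditional, SAP unconditional. Part C: both unconditional. The LLOQ half of the SAP sentence (replace by half the LLOQ) agrees with the protocol; only the ULOQ half differs. The two rules give the same data if the laboratory reports no numerical values above the ULOQ, and the documents do not say whether it does.

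**2. The plan's own figure.** Influenza GMT, 540 per group, ln SD 1.5, margin 1.5, true GMR 1 (protocol Section 2.8.3, Table 5):

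- SE = 1.5 × √(2/540) = 0.0913; ln 1.5 = 0.4055.
- Power = Φ(0.4055/0.0913 − 1.96) = Φ(2.48) = 99.3%. The plan states at least 99%, so it reproduces.

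**3. Effect of the cap at the margin.** Assumptions: normal ln titers with SD 1.5, reference mean 0, coadministration mean ln(1/1.5) = −0.4055, no baseline adjustment, and every capped value would otherwise be available. The ULOQ, c, is placed so that an assumed share of reference values lies above it.

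- Capped mean: m = μΦ(a) − σφ(a) + c[1 − Φ(a)], with a = (c − μ)/σ.
- SE = √[(capped variance in reference + capped variance in coadministration)/540].
- False non-inferiority rate = Φ((difference + 0.4055)/SE − 1.96).

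| Reference share above ULOQ (assumed) | Reference mean | Coadmin. mean | Difference | Capped GMR | SE | Rate (nominal 2.5%) |
|---|---|---|---|---|---|---|
| 1% | −0.0051 | −0.4077 | −0.4026 | 0.669 | 0.0907 | 2.7% |
| 5% | −0.0313 | −0.4214 | −0.3901 | 0.677 | 0.0882 | 3.7% |
| 10% | −0.0710 | −0.4445 | −0.3735 | 0.688 | 0.0850 | 5.7% |
| 20% | −0.1675 | −0.5060 | −0.3385 | 0.713 | 0.0786 | 13.4% |

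The 10% row shows the mechanism. The cap takes 0.0710 from the reference mean but only 0.4445 − 0.4055 = 0.0390 from the coadministration mean, so the difference moves up by 0.0320. Then 0.0320/0.0850 = 0.376, and Φ(0.376 − 1.96) = 5.7%.

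**4. Where the effect vanishes or shrinks.** At a true GMR of 1 the capped GMR is 1.000 for every share. At a true GMR of 0.9 it is 0.901 / 0.904 / 0.909 / 0.918. If only half the values above the ULOQ are available as actual values, the protocol's own rule also caps the other half and gives 2.6 / 3.0 / 3.8 / 5.8%. The SAP's change then accounts for only the remainder.

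**5. RSV-A and SARS-CoV-2.** Per test, the rates are similar: for Part A RSV-A at 378 versus 540 they are about 2.7 / 3.6 / 5.3 / 12%. But SRR on the same antibody is also a co-primary. A joint simulation was run with true GMR 0.667, ln SD 1.5, reference SRR 80%, SRR from uncapped values, a Miettinen-Nurminen bound of −10%, and 378 versus 540. The baseline-to-Day 29 correlation is assumed:

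- At 0.5, both tests pass falsely in roughly 1% of trials at a 5% share and about 2.5% at a 20% share.
- At 0.7, the rate stays below 0.5%.
- At 0.3 with a 20% share, it is about 5%.

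**The case against.** The effect is wholly conditional. It needs laboratory-reported values above the ULOQ, a material share of them, and a true GMR below 1. Nothing in the documents establishes any of these, and at a 1% share the rate barely moves. A single cap is also a defensible convention: it is the same in all three parts, and it gives each Part B Day 29 sample one value. SAP Section 1 says that the SAP supplies data derivations. Whether a quantification-limit rule is a statistical method that needs an amendment under protocol Section 2.8 is open to interpretation. All of this stands. It limits the size of the point but does not remove the contradiction or the missing Section 5 entry.

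Three stronger readings are tempting, and the documents do not support them:

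- *That Part C loses power or departs from the protocol.* Protocol Section 4.8.5.1 caps without condition for GMT, GMFR and GMR, and SAP Section 4.5.1 inherits the same cap. Both sides of the paired comparison are therefore treated alike. A mismatch would arise only if a correction to Section 2.5.1 were applied to one side.
- *That the supportive analysis pooling Study P301 with Group 1 lacks a rule.* SAP Section 2.5.4.2.3 applies the same endpoint definitions and statistical methods as the primary analysis.
- *That the change was never recorded.* The document history is redacted, so an entry there cannot be excluded. Only its absence from Section 5 can be stated.

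**Conclusion.** The discrepancy is certain; its consequence is not. The SAP as written applies a different ULOQ rule from the protocol to the GMT and GMC co-primaries of Parts A and B, and Section 5 does not disclose it. The direction is anti-conservative when the true GMR is below 1.

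A reader might infer that the false-claim rate is 13%. That figure needs an assumed 20% of reference values above the ULOQ, all with usable actual values, and a true GMR exactly at the margin. The documents give no ULOQ and no such share.

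Influenza is the main exposure. Its rate test (SCR) is only a key secondary, tested after the co-primaries have passed, so it cannot block the primary claim. The requirement that all six co-primaries pass gives less protection if only one strain is affected. For RSV-A and SARS-CoV-2 the per-test rates overstate the risk, because the SRR co-primary must also pass. The point is minor to moderate: worth correcting because the correction is cheap, not because a large bias has been shown.

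**What to change.** Choose one of the following, without reference to unblinded titers.

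1. **Restore the protocol rule.** In SAP Section 2.5.1, limit the conversion in Parts A and B to values for which no actual result is reported. Because Section 4.5.1 inherits 2.5.1, add a line there that Part C keeps the unconditional cap of protocol Section 4.8.5.1 for both the BD Day 29 and the Part B Day 29 titers. The costs are that some Part B Day 29 samples may carry different values in the Part B and Part C analyses, and that values above the ULOQ may be less precise.
2. **Keep the single cap.** List and justify it in SAP Section 5, and add a sensitivity analysis of the GMT and GMC co-primaries using actual values where they are reported. This keeps one value per sample in the main analyses, at the cost of one extra analysis. The Section 5 entry should also say why the sponsor considers that no amendment is needed under protocol Section 2.8.

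In either case, tabulate the number of values above the ULOQ by group and assay. That table shows directly whether the issue matters. The total cost is a few SAP lines and a little programming.

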**Incomplete/missing data:**

- Imputation rules for missing dates of prior/concomitant medications and non-study vaccinations are provided in [Appendix C](#).
- Imputation rules for missing dates of prior/concomitant procedures are provided in [Appendix D](#).
- Imputation rules for missing AE dates are provided in [Appendix E](#).

- Other incomplete/missing data will not be imputed, unless specified otherwise.

### Vaccination groups:

The following vaccination groups will be used for summary purposes:

- mRNA-1345 (█ CC1 µg) + placebo
- mRNA-1345 (█ CC1 µg) + Afluria Quadrivalent
- Afluria Quadrivalent + placebo

If a subject receives any dose of mRNA-1345, regardless of the vaccination group the subject is randomized to, the subject will be included in the actual vaccination group received (mRNA-1345 + placebo or mRNA-1345 + Afluria Quadrivalent) for safety and reactogenicity analyses.

All analyses and data summaries/displays for disposition, demographics and baseline characteristics, safety and immunogenicity will be provided by vaccination group using appropriate analysis population, unless otherwise specified. Local solicited adverse reactions will be also summarized by injection content (mRNA-1345, Placebo and Afluria Quadrivalent).

### 2.5.2. Background Characteristics

#### 2.5.2.1. Participant Disposition

The number and percentage of participants in the following categories (analysis sets defined in [Section 2.4](#)) will be summarized by vaccination group as defined in [Section 2.5.1](#) based on Randomization Set:

- Randomization Set
- Full Analysis Set
- Per-protocol Set
- Safety Set
- Solicited Safety Set

The percentages will be based on the number of participants in the Randomization Set (as randomized), except that for the Safety Set and Solicited Safety Set in which the percentages will be based on the number of participants in the Safety Set (as treated).

The number of participants in the following categories will be summarized based on participants screened:

- Number of participants screened

- Number and percentage of screen failure participants and the reason for screen failure

The percentage of participants who screen failed will be based on the number of participants screened. The percentage of participants reporting each reason for screen failure will be based on the number of participants who screen failed.

The number and percentage of participants in each of the following disposition categories will be summarized by vaccination group based on the Randomization Set:

- Received any study injection
- Completed the study
- Prematurely discontinued the study and the reason for discontinuation

The number and percentage of participants by IRT randomized stratum (50 to 59 years, 60 to 74 years and  $\geq$  75 years) will be presented by vaccination group. Also, the concordance between IRT randomized stratum and CRF derived stratum will be tabulated by vaccination group.

A participant disposition listing will be provided, including informed consent, participants who completed the study injection schedule, participants who completed study, participants who discontinued from participation in the study, with reasons for discontinuation. A separate listing will be provided for screen failure participants with reasons for screen failure.

A participant, who has completed the last scheduled procedure on Day 181 (i.e., 6 months after administration of the study injections on Day 1), is considered to have completed the study.

### **2.5.2.2. Demographics and Baseline Characteristics**

Descriptive statistics will be calculated for the following continuous demographic and baseline characteristics: age (years), weight (kg), height (cm), BMI ( $\text{kg}/\text{m}^2$ ). The number and percentage of participants will be provided for categorical variables such as randomized and actual age group (50 to 59 years, 60 to 74 years, and  $\geq$  75 years), gender and race. The summaries will be presented by vaccination group as defined in [Section 2.5.1](#). The summaries will be provided separately based on the Randomized Set, FAS, Safety Set, Solicited Safety Set, PP Set, and Supportive PP Set.

In the Supportive PP Set, participants will be presented by the vaccination group as Group 1 participants from mRAN-1345-P302, participants from mRNA-1345-P301, and Group 2 participants from mRNA-1345-P302. Group 1 participants from mRAN-1345-P302 and participants from mRNA-1345-P301 will also be pooled together as an “Adjusted Group 1” in the summary. The descriptive statistics for age (as a continuous variable), age group (50 to 59

years, 60 to 69 years, 70-79 years, and  $\geq$  80 years), weight, height, BMI, gender, and race will be presented by the vaccination group.

For screened failure participants, age (years), as well as gender, race, ethnicity will be presented in a listing.

In addition, participants with any inclusion and exclusion criteria violation will also be provided in a listing.

